7.6 End of study

End of the study is defined as 6 months after the infusion of CMV pp65-specific T cells of patient number 15 or at time of subsequent DLI of patient number 15.

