Potential benefit of participation to this study is a reduction of the CMV DNA load which may lead to a reduction of development of severe CMV disease or cure of CMV disease. A potential risk of participation to this study is development of acute GvHD.

Contraindications for administration of CMV pp65-specific T cells:

- Life expectation < 6 weeks.
- End stage irreversible multi-system organ failure.
- Acute GvHD overall grade \geq III.
- Treatment with corticosteroids in an equivalent dose of >0.5 mg/kg prednisone.
- No CMV reactivation or CMV disease.

Study endpoints:

- The number of events of acute GvHD, death and all other adverse events.
- The number of CMV-specific T cells at different time points after infusion of CMV pp65-specific T cells.
- The number of complete responses or partial responses of CMV reactivation or CMV disease after infusion of CMV pp65-specific T cells.

Follow-up:

Follow-up of patients will be performed until 6 months after last infusion of CMV pp65-specific T cells or until subsequent DLI, whichever comes first.

In adults:

Weeks after infusion	0	1	2	3	4	5	6	7	8	12	16	20	24
Infusion of cells	x				(x)				(x)				
History and PE	x	x	x	x	x	x	x	x	x	x	x	x	x
Blood	x	x	x	x	x	x	x	x	x	x	x	x	x
CMV DNA	xxx	x	x	x	x	x	x	x	x	x	x	x	x
CMV tetramer	xx	x	x	x	x	x	x	x	x	x	x	x	x
Chimerism							x			x			x
xxx day 0, 1, 2													
xx day 0, 1													

The volume of blood for quantification of CMV-specific T cells by tetramer staining and functional assays (intracellular cytokine staining) is 50 ml.

The volume of bone marrow for chimerism analysis is 10ml.

In children:

Sampling of blood will be according to study protocol “adoptive immunotherapy for adenovirus infections after allogeneic stem cell transplantation in children” as approved by the CCMO. PBMC samples (20ml) will be taken and stored at 2 week intervals for the investigation of the presence and function of CMV-specific T cells until 3 months after last infusion. Blood sampling for this specific protocol will be combined with blood sampling for regular monitoring of the transplantation as much as possible.

Interim analysis:

After the first 3, 6 and 10 patients an interim analysis will be performed by the principal investigator.

Premature termination of the study:

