3. STUDY DESIGN

[figure not shown]
This is an open-label non-randomized phase I/II feasibility study to treat patients with persistent CMV reactivation or CMV disease after alloSCT with administration of CMV pp65-specific T cells generated by use of a CMV pp65 protein-spanning peptide pool.

Patients who receive an alloSCT from a CMV-positive donor are monitored weekly for CMV reactivation using PCR for the detection of CMV DNA. In case of CMV reactivation (defined as CMV DNA load >1000 cp/ml) patients will be treated with antiviral therapy consisting of valganciclovir, ganciclovir or foscarnet.

For patients with CMV reactivation who fail antiviral therapy (defined as **CMV reactivation treatment failure**: persistent CMV DNA load of more than 1000 cp/ml or CMV disease after 2 weeks of adequate treatment with antiviral therapy or relapse of CMV DNA load of more than 1000 cp/ml within 4 weeks after adequate treatment with antiviral therapy or contraindication for treatment with antiviral therapy at the discretion of the physician) or develop CMV disease (organ dysfunction (pneumonitis, enteritis, retinitis, encephalitis, hepatitis, and bone marrow suppression) due to CMV infection), CMV pp65-specific CD4+ and CD8+ T cells will be generated from donor PBMC by overnight in vitro stimulation with pp65 CMV peptide pools. CMV-specific CD4+ and CD8+ T cells will be isolated based on their IFN γ production and administered to the patient directly after quality control. If alloSCT was performed using CD34 positive cell selection and the CD34 negative subfraction has been cryopreserved at a GMP facility, this fraction can also be used for selection of CMV-specific T cells. Antiviral therapy will be continued after infusion of CMV pp65-specific T cells according to standard antiviral treatment protocols at the discretion of the physician.

In case of ongoing CMV reactivation or CMV disease the infusion of CMV pp65-specific T cells may be repeated 2 times with at least 4 weeks interval. The patient will be monitored for adverse events and for effect on CMV DNA load. Follow-up of patients will be performed until 6 months after infusion of CMV pp65-specific T cells or until subsequent DLI, whichever comes first.

Study design for treatment of CMV reactivation and/or CMV disease with allogeneic CMV pp65-specific T cells.

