7.2.3 Investigation during follow-up in adults

- Interim history and physical examination including WHO performance score, weight, signs of toxicity, infection and GvHD daily during hospitalization or weekly for 8 weeks, followed by monthly for 4 more months.
- Blood cell counts, differential, platelet count, sodium, potassium, BUN, creatinine, liver enzymes, total bilirubin, albumin, LDH and glucose weekly for 8 weeks, followed by monthly for 4 more months.
- CMV DNA load at day 1 and 2, followed by weekly for 8 weeks and monthly for 4 more months.

- Quantification of CMV-specific T cells by tetramer staining and functional assays (intracellular cytokine staining) will be performed at the LUMC from blood samples from day 1 and thereafter weekly samples from week 1-8 and monthly samples from month 3-6.
- Assessment of chimerism at 6 weeks, 3 months and 6 months.

Weeks after infusion	0	1	2	3	4	5	6	7	8	12	16	20	24
Infusion of cells	x				(x)				(x)				
History and PE	x	x	x	x	x	x	x	x	x	x	x	x	x
Blood	x	x	x	x	x	x	x	x	x	x	x	x	x
CMV DNA	xxx	x	x	x	x	x	x	x	x	x	x	x	x
CMV tetramer	xx	x	x	x	x	x	x	x	x	x	x	x	x
Chimerism							x			x			x
xxx day 0, 1, 2													
xx day 0, 1													

The volume of blood for quantification of CMV-specific T cells by tetramer staining and functional assays (intracellular cytokine staining) is 50 ml.

The volume of bone marrow for chimerism analysis is 10ml.

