11.3 End of study report

The investigator will notify the CCMO of the end of the study within a period of 8 weeks. The end of the study is defined as the last patients' last control visit. This will be 6 months after the infusion of CMV pp65-specific T cells of patient number 15 or at time of subsequent DLI of patient number 15.

In case the study is ended prematurely, the investigator will notify the CCMO including the reason for the premature termination.

Within one year after the end of the study, the investigator will submit a final study report with the results of the study, including any publications/abstracts of the study, to the CCMO.

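### Follow-up is tied to different infusions in different places, the adult visit grid is too short for re-infused patients, and study end depends on patient 15 alone

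*Protocol*

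**What the plan says.** **Follow-up of each patient.** The Summary (Follow-up) says: "Follow-up of patients will be performed until 6 months after last infusion of CMV pp65-specific T cells or until subsequent DLI, whichever comes first". Section 3 says: "Follow-up of patients will be performed until 6 months after infusion of CMV pp65-specific T cells or until subsequent DLI, whichever comes first". The two differ by one word, which matters because section 5.2 allows two repeat infusions at least 4 weeks apart, with no upper limit on the interval.

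**Adult visits.** The grid in the Summary and in section 7.2.3 has a single time axis counted from infusion. It marks possible repeat infusions at weeks 4 and 8, and its last visit is at week 24. The text of 7.2.3 sets CMV DNA sampling "weekly for 8 weeks and monthly for 4 more months", after samples on days 1 and 2. Nothing restarts the schedule after a repeat infusion. For children, section 7.2.4 does tie PBMC sampling to the last infusion.

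**End of study.** Section 7.6 reads: "End of the study is defined as 6 months after the infusion of CMV pp65-specific T cells of patient number 15". It then names DLI in that same patient as an alternative trigger. The Summary has the same rule. Section 11.3 first defines study end as the final control visit of the last patient and then equates this with the patient-15 rule: "This will be 6 months after the infusion of CMV pp65-specific T cells of patient number 15".

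**The concern.** For a patient infused once, the Summary and section 3 agree. For a re-infused patient they give different end dates, and the adult grid cannot deliver the Summary's rule. Re-infused patients have had repeated exposure to T cells of unknown specificity, which section 6.4 names as the GvHD risk, yet they have the shortest scheduled observation after their last dose.

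The end-of-study rule looks at one patient only. DLI properly ends patient 15's own follow-up, but it is no reason to end anyone else's. DLI is foreseeable here: section 5.3 stores unused donor cells for it.

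The data at stake are the first-listed endpoint in section 7.1 (acute GvHD, death and all other adverse events) and the competing-risk estimates of death in section 9.4. Section 8.2 defines adverse events as those occurring during the trial, so early closure stops the capture of new events in patients still owed follow-up. With 15 patients, a few shortened windows can change the counts.

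**Working it through.** **1. The plan's own time scale.** Section 7.2.3 asks for chimerism at 6 weeks, 3 months and 6 months, and the grid marks it at weeks 6, 12 and 24. The text agrees: 8 weeks + 4 months × 4 weeks = 24 weeks. On the grid, 6 months is therefore 24 weeks. In calendar time it is 365.25 / 2 / 7 = 26.1 weeks.

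**2. Adult grid against the last-infusion rule.** Repeat infusions are marked on the same axis at weeks 4 and 8, so week 0 is the first infusion. Scheduled weeks after the last infusion = 24 − week of last infusion.

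| Last infusion | Scheduled weeks after it | Shortfall against 24 | Grid week needed | Visits after it (weeks) |
|---|---|---|---|---|
| week 0 | 24 | 0 | 24 | 1–8 weekly, then 12, 16, 20, 24 |
| week 4 | 20 | 4/24 = 17% | 28 | 1, 2, 3, 4, 8, 12, 16, 20 |
| week 8 | 16 | 8/24 = 33% | 32 | 4, 8, 12, 16 |

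These use the minimum interval; longer intervals increase the shortfall. After a week-8 infusion, CMV DNA is scheduled only every 4 weeks. A partial response needs at least 2 weeks (section 7.3.2), and one shorter than 4 weeks can contain at most one such sample.

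**3. DLI trigger.** Section 9.2 expects 5 to 7 patients a year. Assuming even spacing, the gap is 365.25 / 7 / 7 = 7.45 weeks to 365.25 / 7 / 5 = 10.44 weeks. If patient 15 has DLI at week d, patient 14 is at gap + d weeks when the study closes. Follow-up still owed to patient 14 after one infusion is 26.1 − gap − d. The documents give no DLI timing, so d is varied.

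| d (assumed) | Patient 14 at closure (weeks) | Still owed, one infusion (weeks) |
|---|---|---|
| 4 | 11.5–14.4 | 11.7–14.6 |
| 8 | 15.5–18.4 | 7.7–10.6 |
| 12 | 19.5–22.4 | 3.7–6.6 |
| 16 | 23.5–26.4 | 0–2.6 |

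If patient 14 had three infusions at minimum intervals, add 8 weeks: at d = 8, 15.7–18.6 weeks are owed. Patient 13 after one infusion is owed 26.1 − 2 × gap − d: 1.2–7.2 weeks at d = 4 and 0–3.2 weeks at d = 8.

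**4. Time trigger without DLI.** If the infusion in section 7.6 means patient 15's first, that patient loses at least 4 weeks (two infusions) or 8 weeks (three). For patient 14 with three infusions at minimum intervals, the loss is max(0, 8 − gap): about 0.5 week at 7 patients a year and 0 at 5 or 6. If it means patient 15's last infusion, patient 15 loses nothing.

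**5. Sample size.** None of this enters the calculation in section 9.3; 15 stands.

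**The case against.** Section 7.6 refers to patient 15's infusion without saying first or last. Read with the Summary it may mean the last, and the opening definition in section 11.3 suggests that nobody meant to stop other patients early. Section 8.3 follows adverse events until they abate or stabilise, so events already under way are not cut off. Sixteen weeks is longer than the 2- and 4-week response windows. Section 3 describes weekly PCR monitoring for recipients from CMV-positive donors, which may fill gaps in the grid.

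Much of this stands, and it rules out several stronger readings that a reader might infer:

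- *Study end is counted from patient 15's first infusion.* The text does not say so. The grid's use of the unqualified term suggests it, but that is an inference.
- *The 6-month trigger cuts off patients 13 and 14.* At planned, even accrual and minimum intervals it costs patient 14 at most about half a week and patient 13 nothing.
- *Re-infused patients lose 38%.* That is (26 − 16) / 26, which sets grid weeks against calendar weeks. On the grid's own scale it is 33%.
- *A 2-week partial response cannot be verified after a third infusion.* Samples at +4 and +8 weeks can support one; only a short response could be missed.

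The objection does not remove the conflict between the Summary and section 3, the adult grid's shortfall, or the DLI trigger, which fails on any reading of the infusion in question. Section 8.3 does not capture new events after closure, and the study schedule does not require the routine PCR.

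**Conclusion.** The follow-up and end-of-study rules contradict each other and need amendment. The adult grid's shortfall follows directly from the text: 4 or 8 of 24 weeks for a last infusion at week 4 or 8. The DLI trigger would close the study with patient 14 at about 11 to 18 weeks after one infusion instead of about 26. That figure rests on evenly spaced accrual of 5 to 7 a year and an assumed DLI at week 4 to 8; the effect shrinks to almost nothing by week 16 and disappears if patient 15 has no early DLI. The time trigger alone mainly affects patient 15's own re-infusions, and only if the first infusion is meant. Late safety events are the main exposure; response assessment is less affected.

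**What to change.** Reconcile the Summary and sections 3, 7.2.3, 7.6 and 11.3:

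- Use one rule for every patient, the Summary's: "Follow-up of patients will be performed until 6 months after last infusion of CMV pp65-specific T cells or until subsequent DLI, whichever comes first". This keeps the patient-level stop at DLI, on which the Summary and section 3 already agree.
- Make the adult grid and the text of 7.2.3 cover that whole period for re-infused patients, and state how visits are counted after a repeat infusion.
- Define end of study, in the Summary, 7.6 and 11.3, as the last follow-up visit of any treated patient. This replaces both the patient-15 date and the patient-15 DLI trigger.

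The cost is amendment wording, a slightly longer study and some extra visits for re-infused patients, part of which routine CMV monitoring may already cover. The sample size does not change.

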8. SAFETY REPORTING

8.1 Section 10 WMO event

In accordance to section 10, subsection 1, of the WMO, the investigator will inform the subjects and the CCMO if anything occurs, on the basis of which it appears that the disadvantages of participation may be significantly greater than was foreseen in the research proposal. The study will be suspended pending further review by the CCMO, except insofar as suspension would jeopardize the subjects' health. The investigation will take care that all subjects are kept informed.

8.2 Adverse and serious adverse events

Adverse events are defined as any undesirable experience occurring to a subject during a clinical trial, whether or not considered related to the investigational drug. All adverse events reported spontaneously by the subject or observed by the investigator will be recorded.

A serious adverse event (SAE) is any untoward medical occurrence or effect that at any dose results:

- in death;
- is life threatening (at the time of the event);
- requires hospitalization or prolongation of existing inpatients' hospitalization;
- in persistent or significant disability or incapacity.

All SAEs will be reported through the web portal *ToetsingOnline* to the CCMO, within 15 days after the sponsor has first knowledge of the serious adverse reactions. SAEs that result in death or are life threatening should be reported expedited. The expedited reporting will occur not later than 7 days after the responsible investigator has first knowledge of the adverse reaction. This is for a preliminary report with another 8 days for completion of the report.

8.2.1 Suspected unexpected serious adverse reactions (SUSAR)

Adverse reactions are all untoward and unintended responses to an investigational product related to any dose administered.

Unexpected adverse reactions are adverse reactions, of which the nature, or severity, is not consistent with the applicable product information.

All SUSARs during this study will be reported to the CCMO and the competent authority through the web portal *ToetsingOnline* within 15 days. For fatal or life-threatening cases, a preliminary report will be send within 7 days, followed by a definite report within 8 days.

8.2.2 Annual safety report

The investigator will submit, once a year throughout the clinical trial, a safety report to the CCMO.

This safety report consists of:

- a report of progress of the study
- a list of all suspected (unexpected or expected) serious adverse reactions, along with an aggregated summary table of all reported serious adverse reactions, ordered by organ system.
- a report concerning the safety of the subject, consisting of a complete safety analysis and an evaluation of the balance between the efficacy and the harmfulness of the CMV pp65-specific T cells.

8.3 Follow-up of adverse events

All adverse events will be followed until they have abated, or until a stable situation has been reached. Depending on the event, follow up may require additional tests or medical procedures, and/or referral to a medical specialist.

9. STATISTICAL EVALUATION

9.1 Statistical design

This is an open-label non-randomized phase I/II feasibility study to treat patients with persistent CMV reactivation or CMV disease after alloSCT with administration of CMV pp65-specific T cells.

9.2 Planned sample size

We aim to include 15 patients. On the basis of the currently performed phase I/II clinical study (LUMC 2004-01) on the treatment of refractory CMV reactivation we expect to include 5-7 patients per year for a period of 3 years.

9.3 Power calculation

We consider the infusion of CMV pp65-specific T cells a success when the response rate is at least 66 % (p_1 ; 2/3 of patients). Based on our historical experience, we estimate the rate of responses with pharmacotherapy alone but without immune intervention to be 30% ($=p_0$) for the targeted patient population. Given the high laboratory effort and associated costs of treatment with CMV pp65-specific T cells, the trial should have a power of 90% (beta-error 0.1). With the usual alfa-error of 0.05, the sample size as calculated according to the standard Fleming design is 15 treated patients under these assumptions. We expect no excess in number of events of acute GvHD, death and all other adverse events.

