4.4 Sample size calculation

We consider the infusion of CMV pp65-specific T cells a success when the response rate is at least 66 % (p_1 ; 2/3 of patients). Based on our historical experience, we

estimate the rate of responses with pharmacotherapy alone but without immune intervention to be 30% ($=p_0$) for the targeted patient population. Given the high laboratory effort and associated costs of treatment with CMV pp65-specific T cells, the trial should have a power of 90% (beta-error 0.1). With the usual alpha-error of 0.05, the sample size as calculated according to the standard Fleming design is 15 treated patients under these assumptions. On the basis of the currently performed phase I/II clinical study (LUMC 2004-01) on the treatment of refractory CMV reactivation we expect to include 5-7 patients per year for a period of 3 years. We expect no excess in number of events of acute GvHD, death and all other adverse events.

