9.4 Statistical analysis

Descriptive statistics and univariate and multivariate analysis will be used to characterize the study population. The endpoint of analysis of treatment toxicity will be done primarily by tabulation of the incidence of side effects with CTCAE grade 2 or more (see Appendix B) or acute GvHD overall grade III or more (see Appendix C). Actuarial competing risk estimates of probability of death will be split by cause of death where a difference will be made between death due to CMV disease and death due to side effects of the treatment. The endpoints of presence of CMV-specific T cells and number of complete remissions and partial remissions of CMV reactivation or CMV disease after administration of CMV pp65-specific T cells will be documented.

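### Sections 4.4 and 9.3 use 66% both as the design alternative and as the bar for success; the stated 90% power belongs to a cut of 8 of 15, while an observed 66% bar has about 60% power

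*Protocol*

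**What the plan says.** Sections 4.4 and 9.3 of the protocol carry the same sample-size paragraph. Its elements in section 9.3 are:

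- **Success:** "We consider the infusion of CMV pp65-specific T cells a success when the response rate is at least 66" %. With its label and gloss, the criterion reads "a success when the response rate is at least 66 % (p_1 ; 2/3 of patients").
- **Null rate:** the response rate on drug treatment alone is taken, from the centre's own experience, "to be 30% ($=p_0$) for the targeted patient population".
- **Power:** "the trial should have a power of 90% (beta-error 0.1").
- **Alpha:** "With the usual alfa-error of 0.05", with no statement of one- or two-sided.
- **Result:** "the sample size as calculated according to the standard Fleming design is 15 treated patients under these assumptions". Section 4.4 says the same: "With the usual alpha-error of 0.05, the sample size as calculated according to the standard Fleming design is 15 treated patients".

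Neither section gives the number of responders at which 30% is rejected. Section 9.4 adds no rule for response; it says that the "number of complete remissions and partial remissions of CMV reactivation or CMV disease after administration of CMV pp65-specific T cells will be documented". The 66% sentence is therefore the only efficacy success criterion in the protocol.

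**The concern.** In a single-stage Fleming design, p1 is the true rate that the trial should be able to detect. The decision cut is a separate quantity and lies between p0 and p1. Here one number does both jobs: 66% is labelled p1, yet the sentence it stands in defines when the treatment counts as a success, and the gloss of two thirds of patients is exactly 10 of 15.

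A bar set at p1 itself is cleared only a little more than half the time when p1 is true. If the sentence is applied to the trial's result, a treatment with the hoped-for response rate fails about 40% of the time, not the intended 10%. The results at stake are 8 and 9 responders: enough to reject 30% under the design, too few under the success sentence. With no cut fixed in the protocol, the label for those results could be chosen after the data are seen, in an open-label trial.

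**Working it through.** **Inputs** (sections 4.4 and 9.3): p0 = 0.30; p1 = 0.66, also given as 2/3; alpha 0.05, sidedness not stated; power 0.90; n = 15.

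**1. Reproduce the sample size.** Fleming normal approximation:

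n = [(z_alpha·√(p0(1−p0)) + z_beta·√(p1(1−p1))) / (p1−p0)]²

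One-sided alpha, p1 = 0.66:

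n = [(1.6449·√0.21 + 1.2816·√0.2244) / 0.36]² = [(0.754 + 0.607) / 0.36]² = 14.29, rounded up to **15**.

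| p1 | One-sided 0.05 | Two-sided 0.05 |
|---|---|---|
| 0.66 | 14.29 → 15 | 17.48 → 18 |
| 2/3 | 13.71 → 14 | 16.79 → 17 |

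The stated 15 is reproduced with one-sided alpha and p1 = 0.66, so the calculation behind the plan is taken to be that one.

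**2. Find the cut that goes with it.** Fleming's cut is the nearest integer to n·p0 + z_alpha·√(n·p0(1−p0)), plus 1:

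15·0.30 + 1.6449·√(15·0.21) = 4.5 + 2.92 = 7.42, nearest integer 7, plus 1 = **8 of 15** (53%).

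**3. Translate the success sentence into a count.** 0.66·15 = 9.9, so at least 10; (2/3)·15 = 10. Either way the observed bar is **10 of 15**.

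**4. Exact binomial properties at n = 15.** P(X ≥ r) at the stated rate:

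| Cut | Type I error (0.30) | Power (0.66) | Power (2/3) |
|---|---|---|---|
| ≥7 | 0.131 | 0.965 | 0.969 |
| ≥8 | 0.0500 | 0.902 | 0.912 |
| ≥9 | 0.0152 | 0.781 | 0.797 |
| ≥10 | 0.0037 | 0.597 | 0.618 |

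Only the cut of 8 matches both the stated alpha and the stated power. The cut of 7 has more power, but a type I error of 0.131.

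**5. Probability of the disputed results.** P(8 or 9 responders | 0.66) = 0.902 − 0.597 = 0.305.

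**6. Limits of the cut of 8.** To more decimals its exact type I error is 0.0500125, just above 0.05. A strict exact one-sided test at 0.05 therefore does not reject at 8 of 15; its cut is 9, with power 0.78. Strict control together with 90% power first occurs at n = 17 with a cut of 9 (type I error 0.040, power 0.916). The two-sided exact 95% interval at 8 of 15 is 26.6% to 78.7% and contains 30%. The exact 90% interval, which corresponds to the one-sided 5% test, has a lower limit of 29.999%, or 30.0% to one decimal.

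**The case against.** The strongest reply is that 66% is explicitly labelled p1 and stands beside p0, alpha, beta and a named design. In that setting p1 is a true rate, the sentence never says observed, and the protocol nowhere writes 10 of 15. Read so, the 90% is right. This stands, and it is why the 60% figure is conditional on reading the sentence as an observed rate. It does not remove the problem: the sentence says when the infusion is to be considered a success, the gloss of two thirds of patients invites the observed reading, and no other criterion corrects it.

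A reader might infer that the power calculation is wrong, or that the trial is too small. The document does not support that: 15 and 90% both reproduce.

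A reader might also count the missing cut, the unstated sidedness and the plain documenting of responses in section 9.4 as faults in themselves. Such detail commonly sits in a statistical analysis plan, which is not shown here, and the named design with its inputs lets a reader recover a one-sided alpha and a cut of 8. The point rests on what the protocol does state. An analysis plan that used 8 of 15 would conflict with the success sentence read as an observed rate.

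Finally, this is a phase I/II feasibility study with response listed last among the endpoints, and no go/no-go action is tied to the 66%. That limits the consequence to how the efficacy result is interpreted and reported.

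**Conclusion.** The concern holds as a conflict between a stated success criterion and a stated power, not as an arithmetic error. Under the one-sided Fleming design that reproduces n = 15, 90% power belongs to a cut of at least 8 of 15. If the success sentence is applied to the observed rate, the cut is 10 of 15, power is 60% at 0.66 (62% at 2/3), and type I error is 0.004 instead of 0.05. The two rules disagree on 8 and 9 responders, an outcome with probability 0.31 when the true rate is 66%.

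This assumes that all 15 treated patients are evaluable for response, that responses are independent with a common rate, and that no efficacy decision is taken at the looks after 3, 6 and 10 patients. If the authors meant 66% only as the true rate under the alternative, the 90% stands, but the sentence still misdescribes p1 as the criterion for success.

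**What to change.** In sections 4.4 and 9.3, replace the success sentence with wording such as:

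> p1 = 66% is the true response rate the trial is designed to detect. By the one-sided Fleming single-stage design (nominal alpha 0.05), p0 = 30% is rejected if at least 8 of 15 treated patients respond (exact type I error 0.0500, marginally above 0.05; power 0.90).

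Report the observed rate with an interval consistent with the one-sided test, such as an exact 90% confidence interval, and note that at exactly 8 of 15 its lower limit is 29.999%. A two-sided 95% interval would contain 30% at 8 of 15 and so appear to contradict the rejection.

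Two alternatives, if the sponsor prefers them:

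- For strict exact control at 0.05 with n = 15, state the cut as at least 9 of 15, with type I error 0.015 and power 0.78.
- If an observed rate of at least 66% really is the bar, keep it and restate the power as about 60%.

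The cost is a change of wording in two sections. None of the three options needs extra patients.
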